Objective: The main objective of this research project is to develop a 4D visual representation model of the human body that allows the analysis of morphological changes resulting from obesity treatment. This 4D model will serve as the core of a body visualization system aimed at improving obesity treatment. The system will provide immersive virtual reality visualizations and personalized simulations of body

evolution during treatment. Furthermore, the effect of these realistic visualizations on patient motivation and adherence to treatment will be studied.

Method: The proposed methodology for obtaining the morphological change representation model presents a significant research challenge. The multidisciplinary intervention combines clinical, psychological, and technological assessments in patients with overweight or obesity. The body is captured in 3D using RGBD sensors to create complete body models, and 4D models reflecting morphological changes over time are generated using advanced deformable registration techniques. These models feed a predictive system that anticipates body evolution under different dietary-nutritional scenarios, facilitating immersive virtual reality visualizations to improve motivation and adherence.

A longitudinal study design is proposed, with two groups (experimental and control) and evaluations at baseline and after six months. Clinical, anthropometric, psychological, nutritional, and technological data will be collected using validated questionnaires and precise measurements.

The analysis includes health indicators, cognitive functions, emotional well-being, and adherence, aiming to validate the system and its impact on motivation and clinical outcomes. Both classical and advanced statistical analyses will be performed, combining traditional methods (t-tests, ANOVA, regressions) with machine learning to predict body evolution, clinical parameters, and adherence. Sample losses will be controlled, and psychological variables will be evaluated as predictors of therapeutic success. Tools such as SPSS, R, Python, TensorFlow, PyTorch, Unity 3D, and Blender will be used.

4. Antecedentes, planteamiento del problema, justificación de la investigación

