Currently, most intervention programs for overweight and obese patients have focused on dietary-nutritional recommendations and promotion of physical activity [8], [9]. While these programs have generally been effective for short-term weight loss, their long-term effectiveness in maintaining weight is limited. Adherence to treatment has been identified as a key factor influencing the duration of treatment and the outcomes of interventions in these patients [10]. Recent studies have shown that high body mass indices (BMI) in obese patients and low adherence to treatment correlate significantly with levels of depression, anxiety, and the presence of cognitive impairments, particularly memory deficits, attention alterations, and poor executive function [3], [11], [12]. These impairments manifest as poorer decision-making, more disinhibited behavior, and inflexible patterns in controlling recurrent thoughts about high-calorie foods [11]. Evidence also shows that long-term nutritional interventions aimed at reducing caloric intake and weight in obese patients produce significant improvements in brain function and reduced oxidative stress when combined with regular physical exercise and adequate adherence to treatment [4]. For instance, a recent study in overweight patients demonstrated that an intensive 6-month nutritional intervention improved participants' general health, BMI, and cognitive function [3].

Given the evidence that lack of adherence is a major cause of intervention failure, improving adherence in patients with overweight and obesity would enhance treatment outcomes and their long-term maintenance, reducing healthcare costs.

Some authors have suggested that nutritional interventions reinforced through technology-based follow-up achieve sustained beneficial effects [12]. A review of 15 studies on interventions for overweight and obese patients found that 60–80% of participants achieved significant long-term weight reduction when interventions were reinforced using interactive multimedia devices [13].

These results highlight how lack of adherence can be improved through the incorporation of image-based techniques (2D) showing the patient's progress during dietary treatment, which enhances the cognitive experience [14]. However, to our knowledge, no studies have yet exploited or quantified the potential of realistic 3D images and virtual reality techniques to reinforce adherence and follow-up over time in overweight and obese patients.

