The project is multidisciplinary, with multiple disciplines collaborating to achieve the common goal of improving motivation and long-term adherence to dietary-nutritional treatments. The research team has a strong track record in 3D image capture and processing, RGB-D sensor calibration and registration [22–27], as well as realistic modeling and visualization. The team also includes professionals in nutrition, psychology, and clinical assessment with experience in national and European projects focused on obesity, treatment adherence, and mental health.

Ethical Considerations

The study was approved by the Research Ethics Committee of the University of Alicante (code UA-2021-11-18, dated 18/11/2021). Prior to study participation and data collection, all participants provided written informed consent. Data will be handled in accordance with the GDPR and LOPDGDD regulations, with anonymization implemented through unique participant codes.

The following sections describe the study design, selected population, eligibility criteria, sampling strategy, sample size calculation, definition of included variables, measurement instruments, monitoring plan, and analysis strategies, along with potential limitations.

Study Design

A prospective longitudinal design with two assessment points was implemented: baseline (pretest) and post-intervention (posttest) after six months of treatment. The study comprised two groups: control and experimental. The control group received nutritional and physical activity education based on recommendations from a nutritionist. The experimental group received a specific, individualized dietary-nutritional intervention program combined with 4D virtual reality. Both groups were assessed for cognitive, clinical, and nutritional outcomes at baseline (pretest) and after six months of intervention (posttest).

To ensure sample representativeness and the generalizability of results, the sample size was calculated using the G*Power 3.1 statistical software. A statistical power of 80%, a medium effect size (0.5), and a significance level (α) of 0.05 were established. Under these parameters, at least 35 participants per group were required to carry out the intervention.

Selected Population

The sample consisted of a total of 133 Spanish volunteers, both men and women, aged between 22 and 67 years ($M = 47.11$ years; $SD = 9.38$). Participants were randomly assigned to one of the two groups (experimental or control).

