- Emotional Eating: Measured with the Emotional Eater Questionnaire (CCE) (Garaulet et al., 2012). Higher scores indicate greater influence of emotions on

food choices and eating habits.

- Prefrontal Symptoms: Assessed using the Prefrontal Symptoms Inventory (ISP-20) (Ruiz et al., 2012); the short version (Pedrero-Pérez et al., 2015) is a self-report questionnaire measuring cognitive, emotional, and behavioral alterations in daily activities.
- Impulsivity: Measured with the Barratt Impulsiveness Scale, BIS-II (Barratt, 1959), comprising 30 items divided into three subscales: cognitive impulsivity (8 items), motor impulsivity (10 items), and non-planning impulsivity (12 items).
- Health-Related Quality of Life: Assessed using the Short Form-12 Health Survey (SF-12) (Ware et al., 1996).
- Depression: Measured using the Beck Depression Inventory (BDI-II) (Beck, Steer & Brown, 1996).
- Life Satisfaction: Measured using the Satisfaction With Life Scale (SWLS) (Diener et al., 1985).

All questionnaire data were collected via Google Forms.

6. Technological and Body Image Variables

- **Body Image:** Assessed using the Body Self-Relations Questionnaire (MBSRQ – reduced Spanish version) (Botella et al., 2009). The instrument contains 45 items divided into two distinct parts: one evaluating general body image and another assessing satisfaction with specific body areas.
- **3D and 4D Images:** The 4D model represents morphological changes over time. Using wide-spectrum, low-cost 3D acquisition technologies (RGB-D sensors), a 4D model was constructed as the core of a human body visualization system, enabling accurate and realistic visualization over time. Throughout the intervention, morphological 3D images of participants were obtained, allowing them to observe their evolution through immersive Virtual Reality (VR) (only the experimental group observed these changes).

Morphological 4D images of participants in each session were captured using the 3D machine, composed of RGB-D devices for 3D image acquisition.

All anthropometric and clinical measurements were collected at the ALINUA Nutrition and Food Clinic, certified as a healthcare center affiliated with the Faculty of Health Sciences at the University of Alicante.

All questionnaires and the neuropsychological battery were administered at two time points: at the start of the program (initial session) and after six months of

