intervention. Anthropometric data and 4D images were also collected at both time points, as well as during individual follow-up sessions conducted to monitor progress and prevent relapses.

Monitoring Plan:

Potential adverse effects arising from the use of Virtual Reality (e.g., dizziness, discomfort, anxiety) and the dietary program (e.g., malnutrition, minor side effects) will be monitored. Adverse events will be recorded in a dedicated database and reported to the Ethics Committee if they are serious or unexpected. Participants will also have the right to withdraw from the study at any time without any consequences.

Data Analysis:

Data analysis is structured in two main phases, encompassing both the development of the predictive model and its clinical and psychological validation. A mixed strategy of advanced quantitative and computational analysis will be applied.

Data Preparation and Preprocessing

- Cleaning of clinical, anthropometric, psychological, and neuropsychological data.
- Standardization and normalization of variables (e.g., assessment scales, physical measurements).
- Coding of categorical variables (e.g., sex, experimental/control group).
- Outlier control and analysis of missing data (intent-to-treat analysis will be applied if missing data exceed 30%).

Classical Statistical Analysis

- **Between-group comparisons (control vs. experimental):**
 - t-tests or ANOVA for continuous measures.
 - Chi-square tests for categorical variables.
 - ANCOVA to adjust for covariates (age, sex, baseline BMI).
- **Longitudinal analysis:**
 - Repeated measures models (repeated measures ANOVA or mixed models).

- Study of changes between assessment points (0 and 6 months).

Multidimensional Predictive Modeling

- Use of multivariate regression models and machine learning to predict:
 - Body evolution (based on SMPL/STAR models).
 - Clinical parameters and psychological well-being.
 - Levels of adherence and motivation.
- Model training using data from the first period (M9) and validation in the second period.

Analysis of Predictive Psychological Variables

- Correlations between cognitive functions and adherence levels.
- Logistic/multiple regression analyses to identify significant predictors of therapeutic success.
- Evaluation of the mediating effect of psychological variables on physical and clinical changes.

Tools and Software

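### Intent-to-treat is made conditional on more than 30% missing data, so observed missingness decides whether a randomised comparison is analysed as randomised

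*Combined protocol and SAP*

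**What the plan says.** Under Selected Population (section 6) the plan states: "Participants were randomly assigned to one of the two groups (experimental or control". Under Data Preparation and Preprocessing, in the item on outliers and missing data, it states in parentheses: "intent-to-treat analysis will be applied if missing data exceed 30" per cent. This is the only mention of intent-to-treat in the document.

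The other relevant text is brief. The Summary says "Sample losses will be controlled", without a method. Potential Limitations names loss to follow-up over the six months, without an expected rate. For longitudinal analysis the plan lists "Repeated measures models (repeated measures ANOVA or mixed models", leaving the choice open and not tying either model to a set of participants. For between-group comparison it lists t-tests or ANOVA, and ANCOVA with age, sex and baseline BMI as covariates. It also lists a study of change from 0 to 6 months.

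On timing, Study Design says "Both groups were assessed for cognitive, clinical, and nutritional outcomes at baseline (pretest) and after six months of intervention (posttest". The end of the variables section says "All questionnaires and the neuropsychological battery were administered at two time points", while "Anthropometric data and 4D images were also collected at both time points, as well as during individual follow-up sessions". Values between baseline and six months are thus stated only for anthropometry and body images.

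**The concern.** Randomisation protects a comparison only if everyone is analysed in the assigned group. Here that protection depends on a quantity seen after the data are in, and the plan is silent on what happens otherwise. Two analysts could follow the text exactly and analyse different sets of people.

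At stake is bias in the between-group comparison, and with it the 0.05 significance level. If the reasons for leaving relate to outcome differently in the two groups, those who remain are no longer comparable. The documents give grounds to take this seriously. The background section says "Adherence to treatment has been identified as a key factor influencing the duration of treatment and the outcomes of interventions in these patients", and only the experimental group was shown its own body changes in virtual reality. Neither statement shows that dropout differed by arm.

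**Working it through.** **The rule.** The 30% is a stated threshold, not a computed figure, so there is nothing to reproduce. Inputs: 133 participants (Selected Population) and the 30% trigger (Data Preparation).

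- 0.30 × 133 = 39.9.
- 39/133 = 29.3%: not triggered, and 133 − 39 = 94 could remain in the analysis.
- 40/133 = 30.1%: triggered.

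This counts participants, which the plan does not specify. Counted by variable, one outcome with 40 missing values would be analysed by intent-to-treat and another with 39 would not. Counted by arm, with arms of 67 and 66 (assumed; arm sizes are not given), 21 lost in the larger arm (21/67 = 31.3%) and 5 in the other would trigger the rule, although total loss is only 26/133 = 19.5%.

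**What leaving people out could do (illustration only).** Assumptions, none from the documents: no true effect; arms of 67 and 66; outcome with SD 1; one follow-up session; correlations of 0.5 (baseline with follow-up), 0.5 (baseline with 6 months) and 0.8 (follow-up with 6 months); equal loss in both arms; random dropout in control; in the experimental arm, dropout more likely with a poor follow-up value, log-odds 1 per SD (range 0.5 to 2).

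Let m be the shift in the mean follow-up value among experimental completers. The spurious group difference is then:

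- t-test at 6 months: 0.8m
- ANCOVA on the outcome's own baseline (slope about 0.5): 0.8m − 0.5 × 0.5m = 0.55m
- change from baseline: 0.8m − 0.5m = 0.3m

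Simulation gives 0.138 SD for the t-test at 20% loss and 0.197 SD at 29%. Hence m = 0.138/0.8 = 0.17 and 0.197/0.8 = 0.25. ANCOVA should then show about 0.55 × 0.17 = 0.09 and 0.55 × 0.25 = 0.14 SD, and change scores about 0.3 × 0.17 = 0.05 and 0.3 × 0.25 = 0.07 SD. Simulation agrees:

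| Completer analysis, log-odds 1 | 20% loss | 29% loss |
|---|---|---|
| t-test | 0.14 SD, 11% type I error | 0.20 SD, 16% to 17% |
| ANCOVA on own baseline | 0.10 SD, 9% | 0.14 SD, 12% |
| Change score | 0.05 SD, 6% | 0.07 SD, 6% to 7% |

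Across log-odds 0.5 to 2, the t-test ranges over 0.07 to 0.21 SD and 7% to 20% at 20% loss, and 0.11 to 0.29 SD and 8% to 31% at 29%. ANCOVA ranges over 0.05 to 0.15 SD and 6% to 14%, and 0.07 to 0.21 SD and 7% to 22%. At log-odds 2 the change score gives 0.08 SD and 7%, and 0.11 SD and 8.5%.

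**Two checks.** With the same dropout mechanism and rate in both arms, the difference is within 0.002 SD of zero and type I error is 5%. Multiple imputation from baseline alone, at log-odds 1, gives 0.099 SD and 8.5% at 20% loss, and 0.138 SD and 11.8% at 29%. These match completer ANCOVA, because imputing from baseline adds no information on the missing 6-month values beyond what that ANCOVA already uses.

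**The case against.** The strongest reply is that the sentence is a parenthesis under preprocessing and that intent-to-treat may be meant loosely, as imputation. That is possible. The rule would still depend on the data, and handling at or below 30% would still be unstated, so the text would still need correcting.

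A second reply is that the size of any bias depends on assumptions and on the test chosen. This stands. The t-test is the least favourable of the three analyses. The change comparison, which the plan also lists, is nearly unaffected under these correlations, although other correlations would change that ranking. It is no general argument for completers.

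Three stronger readings are tempting, and the documents do not support them.

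- A reader might infer that participants will be excluded when 30% or less is missing. The plan implies this but names no such set.
- A reader might infer that the results are biased. That needs dropout that differs by arm in its relation to outcome, and no passage shows it.
- A reader might infer that keeping all randomised participants would itself cut the bias for questionnaires and the cognitive battery. In the illustration it does not: the reduction from t-test to ANCOVA comes from baseline adjustment.

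Where follow-up-session values exist, including them removes the bias in this model, but only because dropout was assumed to depend on exactly those values. The plan gives no schedule for these sessions by arm.

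**Conclusion.** Wrong as written. A randomised comparison should not be analysed as randomised only when missingness passes a threshold, and this threshold also lacks a unit and a stated alternative. The conclusion rests on the wording alone. The illustrated effects of 0.05 to 0.20 SD, with type I error of about 6% to 17% at log-odds 1, show what could happen at losses below the trigger under assumed dropout that differs by arm. They are not estimates for this trial, and with a common mechanism and rate there is no bias. For outcomes measured only at 0 and 6 months, no reduction in bias is claimed from the change of analysis set.

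**What to change.** Delete the 30% condition and state: *All randomised participants are analysed in the group to which they were assigned, whatever the amount of missing data.*

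For between-group comparisons, use the mixed model already listed, or multiple imputation, adjusting for the outcome's own baseline value. The ANCOVA covariates now listed include baseline BMI but not the baseline of each outcome. For anthropometry, include follow-up-session values if their schedule is comparable between arms.

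Because these methods assume data missing at random, add an arm-specific delta-adjusted or tipping-point sensitivity analysis. Justify its range and direction for each outcome before unblinding or analysis. Report completers as a sensitivity analysis only.

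The cost is plan wording and a little more analysis work; no new data are needed. For outcomes measured only twice, bias from informative dropout is examined rather than removed, so the sensitivity analysis cannot be left out.

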- **Statistics:** IBM SPSS Statistics for Windows v.21.0 (IBM Corp, Armonk, NY; 2012), R (latest stable version), and Python 3.11.9 with SciPy and Statsmodels libraries.
- **Machine Learning and Predictive Modeling:** Scikit-learn for classical models and preprocessing. TensorFlow and PyTorch for developing deep learning models and neural networks, including generative networks (GANs) for 3D modeling and multidimensional analysis.
- **Visualization and Clinical Analysis:** Unity 3D for integration and immersive virtual reality visualization, Blender for 3D model manipulation and creation, and internally developed modules for project-specific VR systems.

Potential Limitations

- Possible selection bias (motivated volunteers).
- Loss to follow-up in a 6-month intervention.

- Limited generalizability to the Spanish population with specific sociodemographic characteristics.
- Risk of novelty effect with VR (results may reflect the appeal of the technology rather than the actual intervention effect).

7. Expected impact

In the ICT field, the project will provide methods and algorithms to advance the analysis and prediction of morphological evolution in relation to the parametric predictive model. Additionally, the challenge of acquisition using the RGB-D multi-camera column system and 3D self-portraits for home implementation introduces the development of new techniques based on sparse-view approaches.

In the Health Sciences, the project aims to evaluate the impact of predictive models on patient motivation and adherence to treatment for obesity and overweight. Special emphasis will be placed on the positive effect of realistic predictive visualization of individual body shape on cognitive functioning and psychological well-being.

Scientific and technical impact will be disseminated through presentations at international conferences (ECCV, CVPR, IJCNN in 2022; IUNS-ICN, ICCV in 2023) and publications in high-impact international journals starting in 2023 (IJCV, TPAMI, Pattern Recognition, ASOC, CVIU, EJCN, IJBNP, and JN). Results will also be shared in open-access repositories such as RUA. Data and results will be managed under privacy regulations (LOPDGDD and ENS) and made publicly available on open servers for use by the scientific community, with participants' consent. Developed methods will be shared on repositories such as Bitbucket. Results will also be published on the Tech4Diet website.

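### The planned ANCOVA adjusts for age, sex and baseline BMI but, for outcomes other than BMI, omits the outcome's own collected baseline

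*Combined protocol and SAP*

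**What the plan says.** All the relevant text is in section 6, Methodology.

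- **Between-group comparisons** (Data Analysis, Classical Statistical Analysis): "t-tests or ANOVA for continuous measures", and "ANCOVA to adjust for covariates (age, sex, baseline BMI". The covariate list is closed. Nothing else in the document adds the outcome's own baseline to it.
- **Longitudinal analysis** (same section): "Repeated measures models (repeated measures ANOVA or mixed models" and "Study of changes between assessment points (0 and 6 months". No model terms are given.
- **Baseline collection:** Study Design has cognitive, clinical and nutritional outcomes measured at baseline and at six months in both groups. The end of the variables section says the same for all questionnaires and the cognitive battery, and adds "Anthropometric data and 4D images were also collected at both time points".
- **Missing data** (Data Preparation and Preprocessing): "intent-to-treat analysis will be applied if missing data exceed 30" percent. The analysis set at or below that level is not stated. Potential Limitations lists "Loss to follow-up in a 6-month intervention".
- **Sample size** (Study Design): 80% power, "a medium effect size (0.5", alpha 0.05, at least 35 per group. Selected Population reports 133 participants, randomly assigned.

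No analysis is named as primary. The plan does not say whether the t-test, ANOVA and ANCOVA take the six-month value or the change as the response.

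**The concern.** For a continuous outcome measured before and after treatment, its own baseline is usually the strongest predictor of the final value. The ANCOVA list contains it only when BMI is the outcome; for weight and related body measures, baseline BMI is a plausible proxy. For Mediterranean diet score, CogniFit scores, BDI-II, SF-12, body image, glucose, lipids and blood pressure it is absent. Most of the clinical trial's aims rest on outcomes of this kind.

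Two things are at stake. The first is precision: intervals are wider than the collected data allow. The second is bias, under a condition. The rule on intent-to-treat leaves a completer analysis possible at up to 30% missing. If dropout then depends on the outcome's baseline differently in the two arms, completers no longer have balanced baselines, and an analysis that omits the baseline or merely subtracts it carries that imbalance into the treatment estimate. The arms receive visibly different programmes, so arm-specific dropout is plausible, though not established.

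**Working it through.** **The plan's own figure.** A two-sided, two-sample t-test with d = 0.5, alpha 0.05 and 80% power needs 64 per group, not 35. A paired within-group test needs 34 pairs. The 35 is therefore not reproduced as a between-group size. That is a separate matter, and nothing below depends on it.

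**Inputs.** From the protocol: 133 randomised, effect 0.5, alpha 0.05. Assumed, because the documents are silent: 1:1 allocation (66/67), two-sided testing, 0.5 read as Cohen's d on the six-month SD, equal SDs at both times, pre-post correlation r from 0.5 to 0.8, and 20% loss (133 × 0.8 / 2 ≈ 53 per arm).

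**1. Precision against a change analysis.** In units of the six-month variance, the variance factor is 1 for the unadjusted six-month value, 2(1−r) for the change, and 1−r² with the own baseline as covariate. With two time points, the group-by-time test of a repeated-measures ANOVA is the change test. The interval-width ratio, change to own-baseline, is √[2(1−r)/(1−r²)] = √[2/(1+r)]. Power is from the noncentral t with effective d = 0.5/√factor.

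| r | width ratio | 66/67: change → own baseline | 53/arm: change → own baseline |
|---|---|---|---|
| 0.5 | 1.155 | 82% → 91% | 72% → 84% |
| 0.6 | 1.118 | 89% → 95% | 81% → 89% |
| 0.7 | 1.085 | 96% → 98% | 91% → 95% |
| 0.8 | 1.054 | 99.5% → 99.8% | 98% → 99% |

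**2. Precision against the six-month value.** Unadjusted power is 82% at 66/67 and 72% at 53 per arm. The own baseline cuts the variance by the fraction r².

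If age, sex and baseline BMI predict the outcome, part of this gain is already taken. Treat them as one score explaining a share q of both baseline and outcome. The correlation left for the own baseline is (r−q)/(1−q), and its square is the further variance cut. With q = 0.2 (assumed):

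- r = 0.5: (0.3/0.8)² = 0.141
- r = 0.6: (0.4/0.8)² = 0.250
- r = 0.7: (0.5/0.8)² = 0.391

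Power at 53 per arm rises from 81% to 87%, 91% and 95.5%. At r = 0.3 the cut is (0.1/0.8)² = 0.016, and power moves only from 81% to 82%.

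**3. Bias in completers.** Let dropout be logistic in the standardised baseline in the experimental arm, with higher baselines leaving more, and occur at the same rate but independently of baseline in the control arm. Let D be the resulting completers' baseline gap, found by numerical integration. The six-month comparison is off by rD. The change comparison is off by rD − D = −(1−r)D.

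| Dropout | OR per SD | D (SD) | six-month error, r = 0.5 to 0.8 | change error, r = 0.5 to 0.8 |
|---|---|---|---|---|
| 20% | 2 | −0.129 | −0.06 to −0.10 | +0.06 to +0.03 |
| 20% | 3 | −0.186 | −0.09 to −0.15 | +0.09 to +0.04 |
| 30% | 2 | −0.190 | −0.095 to −0.152 | +0.095 to +0.038 |
| 30% | 3 | −0.270 | −0.135 to −0.216 | +0.135 to +0.054 |

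Simulation of the first row (66/67 randomised, true effect 0.50, 3,000 runs per setting, r = 0.5 to 0.8) gave 0.432 to 0.399 for the six-month comparison, 0.560 to 0.524 for the change, and 0.496 to 0.503 with the own baseline. With q = 0.2, the ANCOVA as listed gave 0.459 to 0.422, so its covariates remove only part of the error.

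A separate simulation with no true effect used 25% dropout, a log-odds slope of 1 per baseline SD in opposite directions in the two arms, and a correlation of 0.3 between BMI and the outcome's baseline. Without the own baseline, type I error was 15.5% at r = 0.5 and 30.0% at r = 0.7; with it, about 5%. When dropout depended on baseline equally in both arms, there was no bias with either model.

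**The case against.** The strongest reply is that the plan already lists mixed models. A likelihood mixed model with arm-by-time means, fitted to everyone with a baseline value, is unbiased under exactly this dropout mechanism, even with baseline means left unconstrained; simulation gives about 0.50 for a true 0.50. That is correct, and it confines the bias to completer analyses. It does not settle the matter. The plan equally allows repeated-measures ANOVA, does not say that the baselines of participants who leave are kept, and names no decisive analysis. The unconstrained mixed model is also less precise: at r = 0.5 its standard error is 0.192, against 0.170 with the own baseline as covariate.

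Second, the bias figures rest on assumed dropout rates, odds ratios and arm differences, and a completer analysis is inferred from the conditional intent-to-treat rule. This stands. The figures show what could happen, not what will. At 20% dropout and odds ratio 2 the errors of 0.03 to 0.10 SD are well inside the change analysis's 95% half-width of 0.24 to 0.39 SD at 53 per arm. The lack of bias with the own baseline also assumes a linear baseline effect with the same slope in both arms.

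Third, a change analysis already reaches 80% power at 66/67 for every r from 0.5 to 0.8, and at 53 per arm falls short only at r = 0.5. This stands too: against change scores the gain matters mainly at r of about 0.6 or lower.

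Fourth, Specific Objective 3 is motivation and long-term adherence. Treatment adherence during the programme has no baseline value, and the variables section names no motivation instrument. The remedy does not reach those outcomes; it does reach Mediterranean diet adherence.

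**Conclusion.** The concern holds. For outcomes other than BMI, the only adjusted between-group analysis that is specified omits a covariate already in hand. With randomisation and no baseline-dependent dropout that differs by arm, the cost is precision alone. Against a change analysis, intervals are 15% wider at r = 0.5, falling to 5% at r = 0.8. Against the six-month value the loss is larger when r is high, less whatever age, sex and BMI already explain. In a completer analysis with arm-specific, baseline-dependent dropout there is also bias, of opposite sign in the two response forms, and the plan has no rule for choosing between them. Own-baseline adjustment removes that part of the bias but not dropout driven by unobserved six-month values. All sizes depend on the assumed r and dropout. This is a weakness that should be corrected; it does not invalidate the trial.

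**What to change.** State whether the between-group tests use the six-month value or the change. For each continuous outcome with a baseline measurement, make the decisive analysis a regression of the six-month value on randomised group, that outcome's own baseline, age, sex and baseline BMI (entered once when BMI is the outcome). A mixed model is also suitable if it takes the outcome's baseline as a covariate or constrains baseline means to be equal across arms. Report the adjusted mean difference with its 95% confidence interval, and do not base conclusions on the unadjusted t-test or ANOVA.

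The cost is one line in the analysis plan, no new data, and at most one degree of freedom per model (none when BMI is the outcome).
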